3.5 Data coding

The data received will be continuous and therefore data coding is not applicable. The units of each variable will be noted beside the variable name in the received data tables.

Data from the main clinical trial database (MACRO) may also be used throughout the analysis for this EME sub study. Please refer to the MARCH Statistical Analysis Plan for further detail.

Doc No: ST06-RD01 Page **7** of **29**

4. **DEFINITION OF TERMS**

Term	Definition
Per protocol population	Per protocol analysis will be undertaken on the population who receive the complete treatment dose.
	Patients randomised to receive usual airway clearance management (UACM) will be excluded from the per protocol analysis if they commence a non-trial mucoactive.
Compliance	Patients who receive ≥90% available doses will be considered as compliant.
Yield Stress	Measure of the amount of stress applied by the rheometer at which the elastic (G') and viscous (G") moduli cross. The amount of force needed to start a flow or break a solid.

Doc No: ST06-RD01 Page **8** of **29**

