6.2 Blinding and Allocation Concealment

The MARCH trial is an open label trial.

Doc No: ST06-RD01 Page **10** of **29**

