7. ANALYSIS PRINCIPLES

The primary analysis will be conducted on outcome data from the per-protocol population. Analyses will be two-sided and tested at an *a priori* significance level of p=0.05.

We will describe baseline characteristics and follow-up measurements using suitable measures of central tendencies; means and medians with the associated standard deviations/95% confidence intervals (CI) and interquartile ranges for continuous data; and frequencies and proportions for categorical data (including binary data).

Primary outcome

To measure percentage mucus solid content (dry-to-wet weight ratio) of sputum at Day 0 and Day 3 following commencement of treatment with carbocisteine and/or hypertonic saline.

Analysis

Percent solids (wt%) of sputum will be assessed by measurement of pre- and post-desiccation weights of sputum aliquots. Higher percentage weight indicates greater mucus solid content and is associated with disease² and lower percentage mucus solid content i.e. more hydrated indicates lower solid content which is associated with a more normal phenotype.

We will assess the sputum percent solids in all 4 patient cohorts on the MARCH trial at day 3 and compare to sample measurements at baseline (before commencement of treatment).

Comparisons will be made between the groups. Analysis of Covariance (ANCOVA) (and post-hoc tests if significant differences are identified), or non-parametric equivalents, will be used to detect difference in means adjusting for baseline values.

Secondary outcomes

The secondary outcome measure post commencement of treatment will be to measure:

- 1. Percentage mucus solid content (dry-to-wet weight ratio) of sputum at Day 7 following commencement of treatment with hypertonic saline and/or carbocisteine
- 2. Sputum elasticity (G') and viscosity (G") (and yield stress, T_c) at Day 3
- 3. Sputum IL-6, IL-8 and 8-isoprostane levels at Day 3
- 4. Sputum elasticity (G') and viscosity (G") (and yield stress, T_c) at Day 7
- 5. Sputum IL-6, IL-8 and 8-isoprostane levels at Day 7

Analysis

Percent solids (wt%) of sputum will be assessed at day 7, as for the primary objective analysis, and compared to sample measurements at baseline (before commencement of treatment).

Comparisons will be made between the groups using ANCOVA (and post-hoc tests if significant differences are identified) will be used to detect difference in means adjusting for baseline values.

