Sputum will also be characterized by its elastic (G') and viscous (G'') moduli in order to determine the yield stress value, T_c , a marker of sputum motion. A high T_c , indicates a greater amount of obstruction in the sample and a lower T_c , indicates a decreased amount of obstruction in the sample.

We will assess the sputum elasticity, viscosity and yield stress in sputum samples obtained from all 4 patient cohorts on the MARCH trial at Day 3 and day 7 and compare to sample measurements at baseline (before commencement of treatment).

Doc No: ST06-RD01 Page **11** of **29**

We will also measure sputum levels of IL-6, IL-8 and 8-isoprostane in sputum samples from all 4 patient cohorts on the MARCH trial at Days 3 and 7 and compare to sample measurements at baseline (before commencement of treatment).

Comparisons will be made between the groups using ANCOVA (and post-hoc tests if significant differences are identified) will be used to detect difference in means adjusting for baseline values.

In addition, all analyses will be undertaken by comparison (i.e. Carbocisteine vs No carbocisteine and Hypertonic saline vs No hypertonic saline).

Doc No: ST06-RD01 Page **12** of **29**

[figure not shown]

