8.4 Trial treatment

- Number of days on treatment, mean(sd) by treatment arm
- Number of doses, mean(sd) by treatment arm
- Treatment compliance, n(%) by treatment arm
- Reasons for termination of study drug, n(%) by treatment arm
- Did not receive allocated treatment, n(%) by treatment arm
- Received treatment of other group, n(%) by treatment arm
- Antibiotic Usage
 - O Number of patients prescribed antibiotics at least once, n(%) by treatment arm
 - Number of days on antibiotics, mean(sd) by treatment arm
 - o Overall dose (antibiotics), mean (sd) by treatment arm
- **Usual Airway Clearance Management**
 - Number of sessions, mean(sd) by treatment arm
- Non-trial mucoactive administration
 - No. patients with non-trial mucoactive administered, n(%) by treatment arm
 - O Name of mucoactive, n(%) by treatment arm
 - o Total number of days on non-trial mucoactive, mean(sd) by treatment arm
- Consent to Continue/Withdrawal of Consent, n(%) by treatment arm
- Protocol Deviations, no. events (%) by treatment arm, no. patients (%) by treatment arm

Will also be presented by comparison

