	·	HTS	Carbocisteine	HTS plus Carbocisteine	UACM
		n=	n=	n=	n=
No. of days on treatment*		xx.x(xx.x)	xx.x(xx.x)	xx.x(xx.x)	xx.x(xx.x)
No. of doses		xx.x(xx.x)	xx.x(xx.x)	xx.x(xx.x)	xx.x(xx.x)
	Compliant	n(%)	n(%)	n(%)	n(%)
Treatment Compliance	Not Compliant	n(%)	n(%)	n(%)	n(%)
	Compliance Rate (%)	xx.x(xx.x)	xx.x(xx.x)	xx.x(xx.x)	xx.x(xx.x)
Did not receive allocated tre	atment	n(%)	n(%)	n(%)	n(%)
Received treatment of other	group	n(%)	n(%)	n(%)	n(%)
	28 days elapsed since randomisation	n(%)	n(%)	n(%)	n(%)
	First successful unassisted breathing (maintained for 48 hours)	n(%)	n(%)	n(%)	n(%)
	Study mucoactive related serious adverse event	n(%)	n(%)	n(%)	n(%)
	Discharge from ICU	n(%)	n(%)	n(%)	n(%)
Reasons for termination of	Death	n(%)	n(%)	n(%)	n(%)
study drug	Discontinuation of active medical treatment	n(%)	n(%)	n(%)	n(%)
	Request from Legal Representative or Patient to withdraw from the trial	n(%)	n(%)	n(%)	n(%)
	Decision from the attending ICU physician that the study drug should be discontinued on safety grounds	n(%)	n(%)	n(%)	n(%)
	Other Reason**	n(%)	n(%)	n(%)	n(%)
	Number of patients with non-trial mucoactives administered at least once	n(%)	n(%)	n(%)	n(%)
	Carbocisteine	n(%)	n(%)	n(%)	n(%)
New trial Barragetine	Hypertonic Saline	n(%)	n(%)	n(%)	n(%)
Non-trial Mucoactive Administration	Heparin (non-anticoagulation purposes)	n(%)	n(%)	n(%)	n(%)
Auministration	N-acetylcysteine	n(%)	n(%)	n(%)	n(%)
	Dornase Alfa	n(%)	n(%)	n(%)	n(%)
	Other**	n(%)	n(%)	n(%)	n(%)
	Number of days on non-trial mucoactive	xx.x(xx.x)	xx.x(xx.x)	xx.x(xx.x)	xx.x(xx.x)
Antibiotic Usage	Number of patients prescribed antibiotics at least once	n(%)	n(%)	n(%)	n(%)

Doc No: ST06-RD01 Page **26** of **29**

MARCH EME Statistical Analysis Plan Final 2.0 26/11/2025

		HTS	Carbocisteine	HTS plus Carbocisteine	UACM
		n=	n=	n=	n=
	Number of days on antibiotic	xx.x(xx.x)	xx.x(xx.x)	xx.x(xx.x)	xx.x(xx.x)
	Overall dose	xx.x(xx.x)	xx.x(xx.x)	xx.x(xx.x)	xx.x(xx.x)
Usual Airway Clearance Management	Number of sessions	xx.x(xx.x)	xx.x(xx.x)	xx.x(xx.x)	xx.x(xx.x)
	Mucoactive administration if ongoing	n(%)	n(%)	n(%)	n(%)
	Ongoing data collection during hospital admission	n(%)	n(%)	n(%)	n(%)
Doct vandomisation	On-going data collection following hospital discharge	n(%)	n(%)	n(%)	n(%)
Post-randomisation withdrawal	Confirmation of vital status	n(%)	n(%)	n(%)	n(%)
witiiuiawai	Use of samples collected to date	n(%)	n(%)	n(%)	n(%)
	Use of data collected to date	n(%)	n(%)	n(%)	n(%)
	Other**	n(%)	n(%)	n(%)	n(%)

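### The per-protocol set drops patients for starting a non-trial mucoactive in the UACM arm only and without a time window, so the primary comparison is open to arm-dependent selection and contamination

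*SAP*

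**What the plan says.** Section 4 of the SAP defines the per-protocol population in two sentences. The first applies to everyone: "Per protocol analysis will be undertaken on the population who receive the complete treatment dose". The second applies to one arm: "Patients randomised to receive usual airway clearance management (UACM) will be excluded from the per protocol analysis if they commence a non-trial mucoactive". Neither sentence limits the exclusion to events before the Day 3 or Day 7 sample.

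Section 7 makes this the headline population: "The primary analysis will be conducted on outcome data from the per-protocol population". The SAP states no analysis of all randomised patients beside it. Section 7 also adds factorial analyses of every outcome: "Carbocisteine vs No carbocisteine and Hypertonic saline vs No hypertonic saline".

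Non-trial mucoactive use is to be reported for every arm. Section 8.4 lists "No. patients with non-trial mucoactive administered, n(%) by treatment arm". The treatment table in Appendix 1 has a row for "Number of patients with non-trial mucoactives administered at least once", with cells for all four arms, and names carbocisteine and hypertonic saline among the possible non-trial agents. Section 6.2 states "The MARCH trial is an open label trial".

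**The concern.** The same event after randomisation is handled differently by arm. A UACM patient who starts a mucoactive leaves the primary analysis. A carbocisteine patient who takes every allocated dose and is also given non-trial hypertonic saline stays in the carbocisteine arm, although in effect on the combination. Because the trial is open label, the decision to start a mucoactive can depend both on the allocation and on how the secretions look. ANCOVA on the Day 0 value cannot fully correct for selection driven by what happens after Day 0.

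The factorial contrasts inherit the problem. The no-carbocisteine group pools UACM, from which starters have been removed, with the hypertonic saline arm, from which they have not. A hypertonic saline patient given non-trial carbocisteine is therefore counted as not having had it. The same holds in mirror image for hypertonic saline.

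The missing time window is a separate defect. Read literally, a UACM patient who starts a mucoactive after the Day 3 sample is dropped from the Day 3 analysis, although that start could not have affected the sample.

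**Working it through.** **Step 1: the rule by arm, as written.**

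| Arm | Must receive complete trial dose | Excluded for a non-trial mucoactive | Use recorded in Appendix 1 |
|---|---|---|---|
| UACM | no trial dose to complete | yes, at any time | yes |
| Carbocisteine | yes | not stated | yes |
| Hypertonic saline (HTS) | yes | not stated | yes |
| HTS plus carbocisteine | yes | not stated | yes |

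**Step 2: the plan's own figures (SAP Section 5).** Difference 1.15, SD 2.3, two-sided 0.05, power 90%. By the normal approximation, n = 2 × (1.960 + 1.282)² × (2.3/1.15)² = 84.1, so 85 per arm, as stated. With the noncentral t, power at 85 per arm is 89.99%. Allowing for 5% dropout, 85/0.95 = 89.5, so 90 per arm, as stated. The target of 1.15 and the SD of 2.3 are the yardsticks below.

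**Step 3: first mechanism, removal of UACM patients with thick secretions.** The SAP gives no commencement rate, so everything here is assumed. Let a fraction f of UACM patients commence, taken as exactly the thickest-secretion end of a normal trait correlated r with Day 3 solids. Removing them lowers the UACM mean by r × 2.3 × φ(z)/(1−f), where z cuts off the top fraction f.

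**Step 4: second mechanism, retention of extra-treated patients.** Assume the same fraction f commences in a single-agent arm and that the extra agent lowers solids by the plan's own 1.15 points. The active mean then falls by f × 1.15, which works the other way. This offset need not apply to combination-arm patients given an agent they already receive.

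| f | φ(z)/(1−f) | Step 3, r = 0.5 | Step 3, r = 0.3 | Step 4 | Net, r = 0.5 | Net, r = 0.3 |
|---|---|---|---|---|---|---|
| 5% | 0.1031/0.95 = 0.109 | 0.12 | 0.07 | 0.06 | 0.07 | 0.02 |
| 10% | 0.1755/0.90 = 0.195 | 0.22 | 0.13 | 0.115 | 0.11 | 0.02 |
| 20% | 0.2800/0.80 = 0.350 | 0.40 | 0.24 | 0.23 | 0.17 | 0.01 |

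(Computed from unrounded values.) At r = 0.5 the first mechanism alone is 11%, 20% and 35% of the 1.15 target. After the offset, the net shift is about 6% to 15% of target at r = 0.5 and close to nil at r = 0.3.

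**Step 5: a check that leaves direction open.** Let c be the share commencing, assumed equal in each arm, and h the baseline-adjusted Day 3 difference between those who commence and those who do not. Excluding commencers from UACM only shifts the comparison by c × h. The sign of h is unknown: it is positive if retained commencers end with thicker sputum and negative if the extra agent more than compensates. With 85 against 85 × (1−c) patients, SD 2.3 and a pairwise t-test:

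| c | size of h | shift | type I error, no true effect | power at 1.15, shift against / for the drug | power if excluded in both arms |
|---|---|---|---|---|---|
| any | 0 | 0 | 0.050 | no shift | – |
| 10% | 1.15 | 0.115 | 0.061 | 80.9% / 93.4% | 86.5% |
| 20% | 1.15 | 0.23 | 0.094 | 68.5% / 95.6% | 82.5% |
| 20% | 2.3 | 0.46 | 0.231 | 44.9% / 99.0% | 82.5% |

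With equal c and h, excluding commencers in both arms cancels the shift. If c differs by arm, which is plausible in an open-label trial, it would not cancel completely.

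**The case against.** The UACM sentence has a sensible reading. That arm has no trial dose to complete, so starting no mucoactive can serve as its adherence criterion. The secondary objectives in Section 1.4 describe the comparator in just those terms. The active arms also carry their own filter, the complete dose, so it is not the case that only UACM loses patients. This explains why the clause is there. It does not remove the problem, because an active-arm patient can satisfy the dose criterion, receive the other agent as well, and remain.

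The appendix tables use the same four columns for every row. A cell for non-trial mucoactives in an active arm shows that use is recorded, not that it is expected. Any restriction on such use may sit in the protocol, which was not available. That limits what can be said about frequency. It does not limit what can be said about the rule.

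A reader might infer that the comparison is biased and that the drug effect is understated. The document does not support either. The two mechanisms oppose each other, no commencement rate is given, and there is no bias if nobody commences or if commencing is unrelated to the outcome. The Step 3 shifts are also an extreme case: they assume that exactly the thickest end of the distribution is removed, and they use the raw SD although the analysis adjusts for baseline.

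**Conclusion.** The asymmetry and the missing time window are plain in the text, and they act on the primary analysis population. The primary comparison and the factorial contrasts are therefore open to arm-dependent selection and contamination. That is a structural weakness, not a demonstrated bias.

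Its size is illustrative only. With assumed commencement of 5–20% and correlation 0.3–0.5, before baseline adjustment, the first mechanism alone moves the UACM mean by about 0.07–0.40 points against a target of 1.15. The second mechanism can cancel part or all of that, and if it dominates, the drug effect against UACM is overstated. Because direction is unknown, the rule cannot be defended as conservative. It should be settled before the data are analysed.

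**What to change.** Amend Sections 4 and 7 as follows.

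- Analyse all randomised patients with matched samples in their allocated arm, with nobody excluded for mucoactive use. Make this the primary analysis, or at least report it beside the per-protocol analysis.
- In the per-protocol set, apply one rule to all four arms: exclude any participant who started a mucoactive not allocated to them before the relevant sample (Day 3 for Day 3 outcomes, Day 7 for Day 7 outcomes).
- Apply the same sets to the factorial contrasts.

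The cost is small. Name, days of use and numbers of patients are already to be reported by arm. The start date of each non-trial agent is also needed, so its availability in the main-trial database should be confirmed. The per-protocol set becomes somewhat smaller: starting from 85 per arm and excluding the same share everywhere, power is 88.5% at 5%, 86.5% at 10% and 82.5% at 20%.

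Some selection remains. Exclusion still happens after randomisation, and a non-allocated agent means any mucoactive in UACM but a shorter list in the combination arm. The per-protocol result should therefore be read as supportive.

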5. SAMPLE SIZE CALCULATIONS

We plan to analyse sputum samples (at Day 0 and Day 3) collected from 340 patients enrolled in the MARCH trial from across participating ICUs. All consecutive patients recruited to MARCH will be approached to participate in the current study. The main MARCH clinical trial is recruiting a target of 1956 patients across the four arms of the study. Therefore, the proposed sample size for this study should be easily achieved given the anticipated recruitment for the MARCH study.

The sample size has been determined with statistical input from the Northern Ireland Clinical Trials Unit to generate significant differences in the primary outcome of percentage mucus solids in sputum samples of MARCH patients. A sample size of 85 in each of our treatment groups will have 90% power to detect a difference in means of 1.15% assuming that the common standard deviation is 2.3% using a two-group t-test with a 0.05 two-sided significance level. This is equivalent to an effect size of 0.5. Assuming approximately 5% dropout we will collect sputum samples from 360 patients recruited to MARCH trial (90 per arm). If the level of dropout is greater than anticipated, we will continue to collect sputum samples (matched Day 0 and Day 3) towards a target of 340 patients. Although there are no examples of mucus solids measurements in patients with ARF, the sample size generated above is based on mucus solid measurements evaluated in patients with cystic fibrosis and chronic obstructive pulmonary disease¹, the closest disease examples to ARF we could find in the literature.

Importantly, there are likely to be missing samples on day 7 due to extubation, discharge, or death. However, we intend analysing these samples as they will still provide important mechanistic information regarding the effect of both drugs on this day.

Doc No: ST06-RD01 Page **9** of **29**

6. RANDOMISATION AND BLINDING

6.1 Randomisation

Patients will be screened and recruited according to MARCH trial procedures.

6.2 Blinding and Allocation Concealment

The MARCH trial is an open label trial.

Doc No: ST06-RD01 Page **10** of **29**

7. ANALYSIS PRINCIPLES

The primary analysis will be conducted on outcome data from the per-protocol population. Analyses will be two-sided and tested at an *a priori* significance level of p=0.05.

We will describe baseline characteristics and follow-up measurements using suitable measures of central tendencies; means and medians with the associated standard deviations/95% confidence intervals (CI) and interquartile ranges for continuous data; and frequencies and proportions for categorical data (including binary data).

Primary outcome

To measure percentage mucus solid content (dry-to-wet weight ratio) of sputum at Day 0 and Day 3 following commencement of treatment with carbocisteine and/or hypertonic saline.

Analysis

Percent solids (wt%) of sputum will be assessed by measurement of pre- and post-desiccation weights of sputum aliquots. Higher percentage weight indicates greater mucus solid content and is associated with disease² and lower percentage mucus solid content i.e. more hydrated indicates lower solid content which is associated with a more normal phenotype.

We will assess the sputum percent solids in all 4 patient cohorts on the MARCH trial at day 3 and compare to sample measurements at baseline (before commencement of treatment).

Comparisons will be made between the groups. Analysis of Covariance (ANCOVA) (and post-hoc tests if significant differences are identified), or non-parametric equivalents, will be used to detect difference in means adjusting for baseline values.

Secondary outcomes

The secondary outcome measure post commencement of treatment will be to measure:

- 1. Percentage mucus solid content (dry-to-wet weight ratio) of sputum at Day 7 following commencement of treatment with hypertonic saline and/or carbocisteine
- 2. Sputum elasticity (G') and viscosity (G") (and yield stress, T_c) at Day 3
- 3. Sputum IL-6, IL-8 and 8-isoprostane levels at Day 3
- 4. Sputum elasticity (G') and viscosity (G") (and yield stress, T_c) at Day 7
- 5. Sputum IL-6, IL-8 and 8-isoprostane levels at Day 7

Analysis

Percent solids (wt%) of sputum will be assessed at day 7, as for the primary objective analysis, and compared to sample measurements at baseline (before commencement of treatment).

Comparisons will be made between the groups using ANCOVA (and post-hoc tests if significant differences are identified) will be used to detect difference in means adjusting for baseline values.

Sputum will also be characterized by its elastic (G') and viscous (G'') moduli in order to determine the yield stress value, T_c , a marker of sputum motion. A high T_c , indicates a greater amount of obstruction in the sample and a lower T_c , indicates a decreased amount of obstruction in the sample.

We will assess the sputum elasticity, viscosity and yield stress in sputum samples obtained from all 4 patient cohorts on the MARCH trial at Day 3 and day 7 and compare to sample measurements at baseline (before commencement of treatment).

Doc No: ST06-RD01 Page **11** of **29**

We will also measure sputum levels of IL-6, IL-8 and 8-isoprostane in sputum samples from all 4 patient cohorts on the MARCH trial at Days 3 and 7 and compare to sample measurements at baseline (before commencement of treatment).

Comparisons will be made between the groups using ANCOVA (and post-hoc tests if significant differences are identified) will be used to detect difference in means adjusting for baseline values.

In addition, all analyses will be undertaken by comparison (i.e. Carbocisteine vs No carbocisteine and Hypertonic saline vs No hypertonic saline).

Doc No: ST06-RD01 Page **12** of **29**

[figure not shown]

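### The primary analysis uses only the per-protocol population, selected after randomisation by rules that differ by arm, and no as-randomised analysis is planned beside it

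*SAP*

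**What the plan says.** Section 7 of the SAP fixes the primary population: "The primary analysis will be conducted on outcome data from the per-protocol population". Section 4 defines it: "Per protocol analysis will be undertaken on the population who receive the complete treatment dose". For the UACM arm it adds that patients "will be excluded from the per protocol analysis if they commence a non-trial mucoactive". The same table gives a separate compliance threshold: "Patients who receive ≥90% available doses will be considered as compliant". It does not say how that threshold relates to full dosing, or over which days doses are counted.

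Section 6.2 records that "The MARCH trial is an open label trial". Section 5 sets the number: "We plan to analyse sputum samples (at Day 0 and Day 3) collected from 340 patients enrolled in the MARCH trial". It allows about 5% dropout (360 collected, 90 per arm). If dropout is higher, collection continues towards 340 patients with matched Day 0 and Day 3 samples.

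The model in Sections 7 and 8.5 is ANCOVA adjusted for the baseline value. The further analyses by comparison (each agent against its absence) name no other population. Section 8.4 tabulates compliance, non-receipt, crossover and non-trial mucoactive use by arm, but only descriptively.

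**The concern.** Randomisation makes the four arms comparable as allocated. The per-protocol rule then removes patients because of what happened afterwards. The SAP's own table of reasons for stopping study drug includes death, ICU discharge, successful unassisted breathing, drug-related serious adverse events and a physician's safety decision. These are prognostic events and may well be related to the state of the secretions.

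The filter also differs by arm. A UACM patient has no study-drug dosing rule to fail and is removed for starting a mucoactive. An active-arm patient is removed for incomplete dosing and, read literally, a combination patient must complete two drugs. Selection that was the same in every arm would largely cancel from a contrast; selection that differs by arm does not.

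The dosing window adds to this. The stopping table lists 28 days since randomisation as a reason for ending treatment, so treatment can run well past Day 3. As worded, a patient with valid Day 0 and Day 3 samples could be excluded for a dose missed after the primary outcome was measured.

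At stake is the reading of the primary result. A difference, or its absence, could reflect who was kept rather than an effect on mucus hydration, and the plan contains no randomised comparison to set beside it.

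**Working it through.** **Inputs from the SAP (Section 5).** "A sample size of 85 in each of our treatment groups will have 90% power to detect a difference in means of 1.15" percentage points, "assuming that the common standard deviation is 2.3" percent, two-sided 0.05, two-group t-test, 5% dropout.

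**Step 1: reproduce the plan's figure.** Standardised difference = 1.15 / 2.3 = 0.5. The normal approximation gives n = 2 × (1.960 + 1.282)² / 0.5² = 84.1, so 85 per arm. The exact t-test solution is 85.03, with power 89.99% at 85. Dropout: 85 / 0.95 = 89.5, so 90 per arm. The stated arithmetic is sound.

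**Step 2: size of a possible selection shift.** The SAP gives no exclusion rate, so these inputs are assumptions: a fraction f of one arm only is excluded, from the thick end of a normally distributed trait that has correlation r with Day 3 solids (SD 2.3). With z the upper-f point of the standard normal and φ its density, the retained mean moves by

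shift = r × 2.3 × φ(z) / (1 − f).

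- f = 10%: z = 1.282, φ(z) = 0.1755, φ(z)/(1 − f) = 0.195
- f = 20%: z = 0.842, φ(z) = 0.280, φ(z)/(1 − f) = 0.350

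| f | r | Shift (wt%) | Share of 1.15 |
|---|---|---|---|
| 10% | 0.3 | 0.3 × 2.3 × 0.195 = 0.13 | 12% |
| 10% | 0.5 | 0.5 × 2.3 × 0.195 = 0.22 | 20% |
| 20% | 0.3 | 0.3 × 2.3 × 0.350 = 0.24 | 21% |
| 20% | 0.5 | 0.5 × 2.3 × 0.350 = 0.40 | 35% |

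These shifts are before baseline adjustment. ANCOVA removes the part that Day 0 solids carry and leaves the rest.

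**Step 3: effect on false positives, as a second illustration.** Assume no true effect, 20% excluded from one active arm, and excluded patients differing from retained ones by d SD. Bias = 0.20 × d SD. The standard error in SD units, with 68 against 85 patients, is √(1/68 + 1/85) = 0.163.

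- d = 0.5: bias 0.10 SD = 0.23 wt%; two-sided error about 9%
- d = 1: bias 0.20 SD = 0.46 wt%; two-sided error about 23%

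These are unadjusted comparisons, so they too are upper illustrations if Day 0 carries part of the selection.

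**Step 4: does power fall?** This is a different scenario, with the same assumed share excluded from every arm. The planned model gains precision from the baseline, so the ANCOVA columns use a standardised difference of 0.5 / √(1 − ρ²), where ρ is an assumed correlation between Day 0 and Day 3.

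| Excluded per arm | n per arm | t-test | ANCOVA, ρ = 0.3 | ANCOVA, ρ = 0.5 |
|---|---|---|---|---|
| 10% | 76.5 | 87% | 90% | 94% |
| 20% | 68 | 82% | 86% | 92% |
| 30% | 59.5 | 77% | 81% | 88% |

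If only one arm lost 10%, 20% or 30%, t-test power would be 88%, 86% or 84%. Power is therefore not the main argument.

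**The case against.** The strongest reply is that this is a mechanistic study. Section 1.3 asks about patients treated with the agents, so an effect under treatment received is a coherent, pre-specified question. That stands as a reason to keep a per-protocol analysis. It does not justify leaving out the randomised comparison: the per-protocol contrast is causal only if, given baseline, excluded patients are exchangeable with those retained, and the SAP neither states nor examines this.

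Second, the outcome is a laboratory weight ratio, so open-label assessment offers little room for bias. That also stands. The open label matters here through adherence, stopping and use of other mucoactives, which are the events that decide membership. The Section 8.4 tables would make such selection visible but would not correct it.

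Third, analysing everyone with both samples does not fully restore the randomised groups. Samples are endotracheal secretions, so a patient extubated or dead before Day 3 will probably have none. This is correct. The change removes selection by adherence and co-medication, not by sample availability.

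A reader might also infer that fewer than 85 per arm will be analysed and that the stated 90% power is lost. The SAP does not support that. It gives no exclusion rate, plans 360 collected, continues towards 340 if dropout is high, and draws on a trial of 1956. Whether per-protocol exclusions count as dropout is left open; the top-up is worded in terms of matched samples and does not mention them.

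**Conclusion.** The concern holds. Followed as written, the plan gives a primary contrast between groups selected after randomisation by rules that differ by arm, with no as-randomised counterpart for any outcome. Baseline adjustment is only a partial protection.

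Under the stated assumptions (exclusion from one arm only, 10% to 20%, correlation 0.3 to 0.5) the shift is about 0.13 to 0.40 wt% before adjustment, 12% to 35% of the target difference. The rate, correlation and direction are all assumed; the true bias could be smaller, larger or in the other direction. The bias figures and the power figures describe different scenarios and should not be added together. A shortfall below 85 per arm remains possible but is not demonstrated.

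The protocol is not at hand and may define an as-randomised set. The explicit choice in Section 7 of the SAP would still need changing.

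**What to change.** 1. In Section 7, make the primary analysis the same baseline-adjusted ANCOVA in all randomised sub-study participants with Day 0 and Day 3 samples, analysed as allocated whatever doses or other mucoactives they received. Add this population to Section 4.
2. Keep the per-protocol analysis as a supportive analysis of the mechanism under adherence.
3. In Section 4, reconcile the full-dosing wording with the 90% compliance definition, and state the days over which doses are counted, so that the per-protocol set is fixed before analysis.
4. State that requiring a Day 3 sample still leaves selection through extubation or death, and report missing Day 3 samples by arm with reasons.
5. In Section 5, say whether the target of 340 counts patients with matched samples or per-protocol patients.

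The cost is SAP wording and one extra run of the same model; no new data are needed. The downside is some dilution of the effect by non-adherence, which the retained per-protocol analysis would show. If the as-randomised effect is still 1.15, analysing all 340 keeps the stated 90% power.
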